6.3 Data Protection

The study database is centrally stored on redundant servers in secured Data Center in Munich, Germany, provided by the eCRF system vendor. The Data Center is certificated and validated, physical access is monitored and only granted to a closed group of employees by the eCRF system vendor.

Electronical access to the system is granted via web application by an identity management service that provides a role and right system and ensures that only authorized users can access a requested resource.

Electronical access to the servers and the database directly is only granted from the local area network of the eCRF system vendor and controlled by the active directory service.

All regulations are noted in the Design Specification document for CVEDC computer system validation documentation.

6.4 Personal Identifiable Information (PII)

All study staff will ensure protection of patient personal data and will not include patient names on any sponsor forms, reports, publications, or in any other disclosures, except where required by laws.

All recorded data is pseudonymized for storage in the central database. Decoding information that would allow identification is only held by the investigator. After database closure, the data will be deleted from the vendor's servers and transferred to the sponsor where it will be stored for 10 years. Regarding to CDISC ODM standard the export format to archive the database is a XML file containing all data and metadata. Data safety, backup and recovery, export and archive are described in the respective SOP document within the CSV documentation by the eCRF vendor.

6.5 Adverse Event (AE), Pregnancy Exposure, and Incident Reporting

All clinical safety data will be collected as outlined in the eCRF. Under ICH GCP and all applicable local regulations and legal requirements, the Sponsor, is responsible for, and undertakes to, assess all clinical safety information arising during the Study (including, but not limited to, that set out in the Definition 6.5.1 in order to generate all safety reports as required.

6.5.1 Definition of adverse events

An adverse event is defined as any untoward medical occurrence in a patient or clinical investigation subject administered a pharmaceutical product and which does not necessarily have a causal relationship with this treatment. An adverse event (AE) can therefore be any unfavorable and unintended sign (including an abnormal laboratory finding), symptom, or disease temporally associated with the use of a medicinal investigational product, whether or not related to the medicinal investigational product.

An adverse drug reaction (ADR) is defined as a noxious and unintended response to a medicinal investigational product related to any dose where at least a reasonable possibility, i.e. the relationship cannot be ruled out.

A Serious Adverse Event (SAE) shall mean any adverse event which meets the following criteria:

- fatal
- life threatening
- disabling or incapacitating
- requires unplanned in-patient treatment or prolongs existing hospitalization
- is a congenital anomaly in the off-spring of the subject
- medically significant or which may require intervention to prevent the previously stated outcomes

For the purposes of this study, all ADRs and SAEs (whether related or not) will be captured in the eCRF and reported to the sponsor as defined in Section 6.5.5.

6.5.2 Data collected for adverse events

Main data being collected may include, but is not limited to:

- Study No
- Centre No

- Subject No
- Event No
- Sender
- Send date
- Event type/description
- Start date
- Outcome
- End date
- Severity/Maximum grade
- Action taken with regard to VH product
- Withdrawal from study as a result of an adverse event/adverse reaction
- Causal relationship to VH product
- Criterion for seriousness

6.5.3 Definition of seriousness

Criteria for seriousness are:

- fatal
- life threatening
- disabling or incapacitating
- requires unplanned in-patient treatment or prolongs existing hospitalization
- is a congenital anomaly in the off-spring of the subject
- medically significant or which may require intervention to prevent the previously stated outcomes

6.5.4 Definition of Outcome of AEs

SAE/ADR outcomes are:

- Recovered/resolved
- Recovering/resolving
- Not recovered/not resolved
- Recovered/resolved with sequel
- Fatal
- Unknown

6.5.5 Reporting of AEs and timelines

The study investigator involved is obliged to collect and report from the time of informed consent to study termination, all ADRs and SAEs.

All ADRs and SAEs will be reported to GSK global safety case management ([contact]) in the form of an electronic safety report within 24hrs of documentation via an automated process.

The safety-related information will be processed according to the legal requirements and country specific regulations to the competent authorities. The recording and reporting of safety data is in a pseudo anonymous format.

6.5.6 Reporting of pregnancy exposures

To ensure subject safety, each pregnancy must be reported to the sponsor within 24 hours of learning of its occurrence. The pregnancy must be followed up to determine outcome (including premature termination) and status of mother and child, which must also be reported to the sponsor. Pregnancy complications and elective terminations for medical reasons must be reported.

Investigators will be provided with necessary “pregnancy exposure” and “pregnancy follow up” forms and supported by CRA and/or ViiV medical affairs in complying with pregnancy reporting procedures. Pregnancies will also be reported to the Antiretroviral Pregnancy Registry (APR) by GSK global safety. The investigator must not report to APR, to avoid duplication.

## Summary of Changes

Version Number	Version Date	Affected Section(s)	Summary of Revisions Made:
1.0	18.07.2023		Initial version
2.0	18.08.2023	Stratification variables; HIV TSQs	Specification of stratification variables and correction of HIV TSQs analysis

### 3 Abbreviations and Definitions

Abbreviation/Definition	Description
2DR	Two drug regime
3DR	Three drug regime
ADR	Adverse drug reaction
AE	Adverse event
ALT	Alanine Aminotransferase
ART	Antiretroviral therapy
AST	Aspartate Aminotransferase
BL	Baseline
BMI	Body mass index
CDC	United States Centers for Disease Control and Prevention (CDC); here: CDC Classification System for HIV Infection
CRF	Case Report Form
DA	Data analyses
DM	Data management

DMP	Data management plan
DOCX	Microsoft Word file
DTG	Dolutegravir
DVP	Data validation plan
EMF	Enhanced meta file
eGFR	Estimated glomerular filtration rate
FDA	U.S. Department of Health and Human Services, Food and Drug Administration
FPE	First participant enrolled
FU	Follow-up
GSK	GlaxoSmithKline
HIV	Human immunodeficiency virus
HIVTSQs	Treatment Satisfaction Questionnaire
HRQL	Health related quality of life
INSTI	Integrase inhibitor
LOCF	Last observation carried forward
LPE	Last participant enrolled
LPFV	Last participant first visit
MedDRA	Medical Dictionary for Regulatory Activities
MUC	MUC Research GmbH
NIS	Non-interventional study
NNRTI	Non-nucleosidic reverse transcriptase inhibitor
NRTI	Nucleoside reverse transcriptase inhibitor
PDF	Portable document format
PNG	Portable network graphics
RPV	Rilpivirine
SAE	Serious adverse event
SAP	Statistical Analysis Plan
SD	Standard deviation
SDM	Symptoms Distress Module
ViiV	ViiV Healthcare

## 4 References

### 4.1 Internal

- SOP\_Proc\_StatAnalysis
- SOP\_Guidance\_for\_Stata\_Programming
- SOP\_Stata\_ProgVal

### 4.2 External

- 2.1\_JUNGLE\_protocol\_final\_14Mar2018
- a\_208982\_Protocol\_Amendment 1\_07Dec2018

## 5 Introduction

Introductory note:

Chapters 5 (*Introduction*), 6 (*Objectives*), 7.1, 7.2, and 7.3 (*Study design and participant enrollment, Sample size, and Participant enrollment: inclusion and exclusion criteria*) are extracted from the JUNGLE study protocol (Amendment 1; eTrack ID: 208982).

JUNGLE is a non-interventional single-arm study (NIS). This prospective, multicenter NIS will evaluate antiretroviral efficacy and tolerability of JULUCA, a novel two-drug combination of dolutegravir, an HIV-1 integrase strand transfer inhibitor (INSTI), and rilpivirine, an HIV-1 non-nucleoside reverse transcriptase inhibitor (NNRTI), in a real-world setting in Germany.

Recruitment target is a total of N=250 treatment-experienced and virologically suppressed patients, with a minimum of 180 participants. Inclusion into the study is independent from prescription of JULUCA. Eligible subjects will be followed up for approximately 3 years collecting information that can be obtained in routine clinical care.

The sample is deliberately non-stratified to reduce limitations on recruitment. The JUNGLE study is not hypothesis testing, but rather of descriptive nature; statistical analysis will be of descriptive nature only.

## 6 Objectives

Annotation: Timepoints for primary and secondary objectives are specified in section 11. *Planned Analyses*.

### 6.1 Primary Objective

Evaluate sustainability of antiretroviral suppression in suppressed patients using JULUCA in routine clinical care in Germany to evaluate antiretroviral efficacy of the novel 2-Drug Regimen (2DR) of JULUCA

### 6.2 Secondary Objectives

- Gain an understanding of the major relevant patient populations for JULUCA in Germany, in terms of patient characteristics and history
- Describe real-life efficacy profile of JULUCA
- Describe real-life tolerability profile of JULUCA as measured by discontinuation rates due to adverse drug reactions (ADRs) and overall number of serious adverse events (SAEs)
- Analyze the development of viral resistance by evaluating available resistance data in case of virologic failure
- Describe impact on lipid metabolism
- Evaluate medical need for a substance and/or class sparing treatment regimen by assessing the reason for switching to JULUCA
- Describe participants' treatment satisfaction and symptom distress based on validated questionnaires
- Evaluate number of monitoring measures and referrals to other specialists

## 7 Study methods

### 7.1 Study design and participant enrollment

- Prospective, non-interventional, single-arm, multi-center study of participants with a clinical indication for HIV-1 therapy in routine clinical care with an observational period of 3 years.
- Investigators may enroll eligible subjects according to their availability and accessibility. The sample is deliberately nonstratified to reduce limitations on recruitment. This nonprobabilistic convenience sampling may not ensure for the sample group to be a true representative of the population without sampling error.
- Inclusion into the study is independent from prescription of JULUCA.
- Data collected during routine clinical care will be documented as study visits. This may include data from hospital records, clinical charts, electronic patient records or laboratory notes.
- Once a year and additionally at first follow-up visit, participants will be asked to complete the HIV Symptom Distress Module and the HIV treatment satisfaction questionnaire on a voluntary basis
- At each visit, participants will be prompted to give an estimate of their level of adherence in a single-item question

### 7.2 Sample size

Sample size was calculated based on the assumption of an antiviral efficacy of 90% (defined as VL <50 c/ml) and a max. study dropout rate of 30% over a period of 3 years. To reach a level of confidence of 95% with a target width of 0.1 (10%), a minimum of N=158 subjects are needed at the end of the study. When max. drop-out rate is included, a minimum number of N=226 subjects are needed. Therefore, the recruitment goal is N=250. If 250 participants cannot be recruited within 6 months, recruitment period may be extended until a minimum number of 180 participants is reached.

### 7.3 Study population: Inclusion and exclusion criteria

#### 7.3.1 Inclusion criteria

- ≥ 18 years of age
- Documented HIV-1 infection
- Virologically suppressed (HIV RNA < 50 c/mL for at least 6 months)
- Prescription for JULUCA was issued independently from entering this study
- Ability to understand informed consent form and other relevant study documents

#### 7.3.2 Exclusion criteria

- Any contraindication according to JULUCA SmPC
- Documented viral load > 50 c/ml at any timepoint within 6 months prior to inclusion into this study
- History of treatment failure
- Known or suspected substitutions associated with resistance to any NNRTI or INSTI
- Any antiretroviral therapy for the treatment of HIV-1 in addition to JULUCA
- HBV-coinfection
- Current participation in the ongoing non-interventional study
- TRIUMPH (study number: 202033) or any interventional clinical trial irrespective of indication
- Previous participation in clinical trials involving JULUCA

## 7.4 Flow chart

For details see 11.2 and 11.3.

Forms	Visit	Enrollment visit	Baseline visit (=last visit before start of therapy with DTG+RPV)	(Routine-based) Follow-up visits until end of study	Study discontinuation	Independent of visits, continuous reporting
Informed consent		X				
In-, exclusion criteria		X				
Date of start with JULUCA			X			
Demography			X			
HIV/ART history			X			
Anamnesis (drug adherence, pregnancy, vital signs incl. weight)			X	X	X	
Laboratory parameters (hematology, metabolic parameters and clinical chemistry, transaminases and lipids)			X	X	X	
Comedication			X	X	X	
Comorbidities			X	X	X	
Referrals to another medical specialist			X	X	X	
Resistance mutation testing			X	X	X	
HIV TSQ			X	X	X	
HIV SDM			X	X	X	
Date & reason of study discontinuation					X	
Post ART					X	
ADR/SAE						X
HIV-related characteristics (laboratory parameters)						X

## 7.5 Data management and analyses

The data management analyses will be performed by MUC Research GmbH after the finalization and approval of this SAP document by the sponsor and after data lock (following final reconciliation of data bases, Data Review Meeting) and database lock.

## **8 Analysis population, analyses sets**

### **8.1 Modified Full Analysis Set**

After closure of the database, all analyses will be based on the modified Full Analysis Set (mFAS) defined as follows:

- all participants of the FAS without
  - violation of in- or exclusion criteria (screening failures)major protocol violations (see 9)
- participants with protocol deviations may be excluded upon decision of the data review meeting.

The decision on the mFAS set will be made during the data review meeting prior to database lock.

A listing of all protocol violations and deviations will be produced, including the assessment major/minor and the procedure/consequence which followed.

### **8.2 Effectiveness Set**

Following the primary endpoint, the effectiveness set comprises all participants of the mFAS except for

- participants lost to follow up (irrespective of last HIV-RNA level)
- participants on drug but without HIV-RNA in time window.

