### 10.3 Statistical methods

- Missing data:

For descriptive statistics, analyses will be based on valid (or observed) data per parameter (resulting in different sample sizes).

The following data imputations will be performed:

HIVTSQs (10 item version) score: If  $\leq 3$  items in one questionnaire are missing, mean of all other non-missing items of this participant at this visit will be imputed. If  $> 3$  items in one participant at a visit are missing, the whole score of this participant is set to missing

For HIVTSQs individual item analysis no data will be imputed. However, the basis for this analysis will be the set of participants who completed the questionnaire at both time points

No further data imputation is performed.

- The frequency and proportions (based on the non-missing sample size) of observed levels will be reported for categorical measures.
- Continuous variables will be summarized using the following descriptive statistics: n (non-missing sample size), mean, standard deviation, median, selected quantiles (lower quartile (25%), upper quartile (75%)), minimum and maximum.
- All analyses will be performed respective analyses sets and the subgroups specified in 11.1.2

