## 11.3 Follow-up (FU) data

### 11.3.1 Primary Endpoint at year 3 follow-up

Primary endpoint is the proportion of participants with sustained virologic suppression, defined as HIV-RNA <50 copies/mL or if between 50-200 copies/mL with a subsequent next available measurement\* (within 120 days) <50 copies/mL at year 3 follow-up.

(\*Any subsequent measurement will be accepted as a consecutive measurement as long as measured no later than 120 days after the initial measurement. If no subsequent HIV-RNA measurement is performed within 120 days this is scored as a confirmed HIV-RNA ≥200 copies/mL)

Listing for participants excluded for primary endpoint analyses for the following reason:

- Lost to follow-up

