### 11.3.5 Study discontinuation prior to year 3 follow-up

- Proportion of participants discontinued the JUNGLE study prior to year 3 follow-up visit
- Reasons for study discontinuation (N, %) - incl. listing of 'other' reason
- Participants discontinued due to virologic reasons: LOCF HIV-RNA copies/mL (listing)
- ART regimes after discontinuation of the JUNGLE study (N, %)

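### SAP 8.2 drops participants lost to follow-up even if they have a valid year 3 HIV-RNA, and no planned sensitivity analysis shows how far the exclusion affects the primary result

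*SAP*

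**What the plan says.** SAP 8.2 ties the set to the primary endpoint: "Following the primary endpoint, the effectiveness set comprises all participants of the mFAS except for" two groups. The first is "participants lost to follow up (irrespective of last HIV-RNA level"; the second is "participants on drug but without HIV-RNA in time window". SAP 11.3.1 confirms that the first group leaves the primary analysis and appears only in a listing: "Listing for participants excluded for primary endpoint analyses for the following reason", the reason given being loss to follow-up. The listing is not said to include the last HIV-RNA or its date.

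Three other places bear on the same participants:

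- SAP 10.2 takes, for year 3, the assessment nearest day 1095 among those in days 1005 to 1185 made while the participant is on treatment and on study.
- The footnote in SAP 11.3.1 covers a value that is not followed up: "If no subsequent HIV-RNA measurement is performed within 120 days this is scored as a confirmed HIV-RNA ≥200 copies/mL".
- SAP 10.3, after the HIVTSQs rule, states: "No further data imputation is performed". Protocol section 4 likewise rules out substituting or recoding missing data, and leaves the data sets to the SAP.

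A last-value output exists in SAP 11.3.5, for one group only: "Participants discontinued due to virologic reasons: LOCF HIV-RNA copies/mL (listing". The protocol's primary endpoint (3.4.1) contains no exclusion for loss to follow-up. Neither document defines the term.

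**The concern.** There are two problems.

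First, 8.2 makes exclusion depend on what happens after the year 3 measurement. A participant can supply the value that the endpoint asks for and then be removed because of a later event. If that value was viremic, 8.2 removes a result that 11.3.1 scores as a failure. If it was suppressed, 8.2 removes a success.

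Second, for participants lost with no in-window value, the plan treats the year 3 result as unknown and says nothing more. The objective is sustained suppression, and loss may be related to it. Protocol 6.2.3, for example, directs withdrawal after a known period of non-adherence of more than 28 days, so the study itself links adherence with leaving. With dropout planned at up to 30%, a reader needs to see how far the headline proportion depends on those who left, and no planned table or listing shows this.

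**Working it through.** **Step 1: the plan's own figures.** Inputs from protocol 3.5: 90% suppressed, 95% confidence, total interval width 0.10, 30% dropout. With an exact (Clopper-Pearson) interval, the smallest n with width at most 0.10 is 158 (width 0.0997 at 158, 0.1001 at 157). Then 158 / (1 − 0.30) = 225.7, rounded up to 226. Both figures reproduce. The planning already leaves dropouts out of the denominator, so the sample size does not depend on the wording of 8.2.

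**Step 2: the sections side by side.** The cases are hypothetical. In the first two, assume the value is the one nearest day 1095.

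| Case | 10.2 | 11.3.1 | 8.2, read literally |
|---|---|---|---|
| <50 copies/mL at day 1010, then lost | value selected | suppressed | excluded |
| 60 copies/mL at day 1010, no retest within 120 days, then lost | value selected | scored as confirmed ≥200, not suppressed | excluded |
| 50,000 copies/mL at day 980, then lost, nothing in window | nothing to select | no year 3 value | excluded |
| 50,000 copies/mL at day 980, still on drug, nothing in window | nothing to select | no year 3 value | excluded (second group) |

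The first two rows conflict. The last two do not: a value outside the window is not used for anyone, lost or retained. The contradiction is therefore confined to participants with an in-window value.

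**Step 3: size of the unknown part.** The documents do not give the number lost to follow-up or the share viremic when last seen. Assumptions: N = 250 (the recruitment goal), L = 25 to 50 lost with no in-window value, no other exclusions, p = 0.90 suppressed among the other N − L, and a fraction v = 5% to 15% of those lost viremic at last measurement.

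- Observed data only: p(N − L) / (N − L) = 90%, whatever L is.
- All lost counted as not suppressed: p(N − L) / N.
  - L = 25: 0.90 × 225 / 250 = 202.5 / 250 = 81%.
  - L = 50: 0.90 × 200 / 250 = 180 / 250 = 72%.
- Lost classified by last value: [p(N − L) + (1 − v)L] / N.
  - L = 25, v = 5%: (202.5 + 23.75) / 250 = 90.5%; v = 15%: (202.5 + 21.25) / 250 = 89.5%.
  - L = 50, v = 5%: (180 + 47.5) / 250 = 91.0%; v = 15%: (180 + 42.5) / 250 = 89.0%.

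The last-value result equals the observed 90% when 1 − v = p, that is, when v = 10%. Below that share the exclusion understates suppression; above it, the exclusion overstates it.

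**The case against.** The strongest defence is that the rule is prespecified and does not depend on outcome: it removes lost participants last seen suppressed as readily as those last seen viremic. It also fits the no-imputation statements in protocol section 4 and SAP 10.3, and the study is descriptive (protocol 3.6). This stands as a reason to keep the observed-data analysis as primary. It does not explain removing someone whose year 3 value was observed, since nothing is imputed there.

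A definition might also remove the first problem. SAP 11.3.5 frames discontinuation as occurring before the year 3 follow-up, so a participant with an in-window value might never be classed as lost. That reading is possible, but neither document states it.

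Transparency is partly covered. SAP 11.3.5 gives counts by reason for discontinuation and 11.3.1 lists the lost participants, so a reader could work out the all-lost-as-failure bound by hand. The last-value version could not be recovered from the planned outputs.

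Four stronger readings are tempting and are not supported:

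- That viremia followed by loss is never counted as a failure. SAP 11.3.2 counts two consecutive values of at least 200 copies/mL from baseline to year 3, in both the rebound endpoint and the composite. SAP 8.1 bases analyses generally on the mFAS, which does not exclude lost participants. The gap concerns the primary endpoint.
- That the exclusion can only raise the reported proportion. That looks at the viremic losses alone; step 3 shows the direction turns on a share the documents do not give.
- That viremic losses should stay in the denominator while suppressed losses are dropped. That rule selects on outcome and builds in a downward bias.
- That all planned dropouts (30% of 250 is 75) leave the denominator. SAP 8.2 removes those lost to follow-up and those on drug without a value, not participants who stopped for other recorded reasons.

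**Conclusion.** The point holds for the primary endpoint, in two parts. As worded, SAP 8.2 contradicts 10.2 and 11.3.1 for any participant with an in-window year 3 value who is later recorded as lost; how many that affects cannot be known from the documents. For participants lost without such a value, the exclusion is symmetric and the direction of bias is not established, but the plan gives no view of how much the result depends on it.

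Under the step 3 assumptions, an observed 90% sits beside a lower bound of 81% to 72%, which is 9 to 18 points lower, against a target interval width of 10 points. The last-value result stays within about 1 point of 90%. The bound is an extreme case, not an estimate, and every figure moves with the assumed number lost and share viremic. The gap between the two results is the reason to report both. The plan should be changed, but the primary analysis need not be replaced.

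**What to change.** 1. **SAP 8.2.** Define lost to follow-up and limit the first exclusion to participants lost without an HIV-RNA in the year 3 window. State that anyone with an in-window value selected under 10.2 is kept and scored on it under 11.3.1, including the 120-day footnote, whatever happens later.
2. **SAP 11.3.1 listing.** Add the last on-treatment HIV-RNA and its date for each excluded participant.
3. **Sensitivity results.** Keep the observed-data analysis as primary. Beside it, report one result with all participants excluded as lost counted as not suppressed, and one classifying them by last HIV-RNA. Say how a participant with no on-treatment value is handled: everyone should enter suppressed, so using the baseline value would count that participant as a success.
4. **SAP 10.3.** Add that these two results are labelled sensitivity analyses and are the only exception to the no-imputation rule, and note the same against protocol section 4.

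The cost is a few sentences of SAP text, two listing columns and two lines in the primary table. The plan already collects HIV-RNA results continuously (SAP 7.4), so no new data are needed. The downsides are a longer table and a published lower bound less favourable than the headline. If the database is already locked, the additions should be labelled as made after lock.

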## 10 Statistical Methods

### 10.1 Definition of analysis time window

### 10.2 Year 1, 2, and 3 follow-up windows

**Year 1 follow-up window** is defined as 9 to 15 months [275 days; 457 days] after the therapy start. This window applies to all variables incl. patient reported outcomes.

Rule for two or more assessments in the time window:

The closest available assessment to year 1 (365 days) after therapy start while the participant is on treatment and continued on study within the time window.

**Year 2 follow-up window** is defined as 21 to 27 months [640 days; 822 days] after the therapy start. This window applies to all variables incl. patient reported outcomes.

Rule for two or more assessments in the time window:

The closest available assessment to year 2 (730 days) after therapy start while the participant is on treatment and continued on study within the time window.

**Year 3 follow-up window** is defined as 33 to 39 months [1005 days; 1185 days] after the therapy start. This window applies to all variables incl. patient reported outcomes.

Rule for two or more assessments in the time window:

The closest available assessment to year 3 (1095 days) after therapy start while the participant is on treatment and continued on study within the time window.

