### 11.3.2 Secondary Endpoints (EPs) (analyzed at years 1, 2 and 3 follow-up, unless otherwise stated)

- Primary endpoint is the proportion of participants with sustained virologic suppression, defined as HIV-RNA <50 copies/mL or if between 50-200 copies/mL with a subsequent next available measurement\* (within 120 days) <50 copies/mL at years 1 and 2 follow-up
- Proportion of participants with HIV-RNA <50 copies/mL at years 1, 2 and 3 follow-up
- Proportion of participants with low level viremia, defined as a HIV-RNA measurement ≥50 copies/mL and <200 copies/mL at years 1, 2 and 3 follow-up
- Proportion of participants with virologic rebound, defined as two consecutive HIV-RNA measurements ≥200 copies/mL from baseline until year 3 follow-up
- Proportion of participants with two consecutive measurements of ≥200 copies/mL, or treatment switch due to virologic failure or due to intolerance as determined at the discretion of the physician from baseline until year 3 follow-up
- Number of HIV monitoring measures (HIV-RNA measurements) [normalized to participant years] from baseline until year 3 follow-up
- Number and frequency of serious adverse events (SAEs) from baseline until year 3 follow-up [normalized to participant years] (see 11.3.10)
- Number and frequency of adverse drug reactions (ADRs) from baseline until year 3 follow-up [normalized to participant years] (see 11.3.10)
- Adherence to therapy [refers to missed monthly doses] at years 1, 2 and 3 follow-up (see 11.3.4)
- Change in lipid laboratory values at years 1, 2 and 3 follow-up (see 11.3.8.3)
- Change in treatment satisfaction [HIV Treatment Satisfaction questionnaire] at years 1, 2 and 3 follow-up (see 11.3.12.2)
- Change in symptom distress [HIV Symptom Distress Module questionnaire] at years 1, 2 and 3 follow-up (see 11.3.12.1)
- Reason for switch to DTG+RPV (see 11.3.5)
- Referral to other medical specialist from baseline until year 3 follow-up (see 11.3.7)
- Proportion of participants with resistance testing from baseline until year 3 follow-up
- Listing of detected resistance-associated mutations from baseline until year 3 follow-up
  - Listing of new (emerging) resistance-associated mutations, incl. resistance-associated mutations detected prior to treatment with DTG+RPV and last HIV-RNA

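### The SAP gives no year-3 primary score to participants who stop DTG+RPV before the window, and its passages point to different denominators

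*SAP*

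**What the plan says.** Four parts of the SAP bear on who enters the year-3 primary proportion and how they are scored.

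- **8.2 (effectiveness set).** Two groups leave the set. The first is "participants lost to follow up (irrespective of last HIV-RNA level", closed by a bracket. The second is "participants on drug but without HIV-RNA in time window". Participants known to be off the drug are not mentioned.
- **11.3.1 (primary endpoint).** Success is HIV-RNA below 50 copies/mL at year 3, or 50 to 200 with the next value within 120 days below 50. Stopping treatment is not addressed. Under "Listing for participants excluded for primary endpoint analyses for the following reason", loss to follow-up is the only reason given.
- **10.2 (windows).** The year-3 window is days 1005 to 1185. The value used is the one closest to day 1095 "while the participant is on treatment and continued on study within the time window". That condition is printed beneath the line "Rule for two or more assessments in the time window".
- **10.3 (missing data).** "The frequency and proportions (based on the non-missing sample size) of observed levels will be reported for categorical measures". Apart from the treatment satisfaction score, "No further data imputation is performed". Protocol section 4 likewise rules out substituting or recoding missing data.

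The definition is reused for the earlier time points in 11.3.2 ("within 120 days) <50 copies/mL at years 1 and 2 follow-up"), also without a rule for stopping.

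The plan expects such participants. Section 11.3.5 lists those who discontinue for virologic reasons with their last HIV-RNA. One composite endpoint in 11.3.2 includes a treatment switch for virologic failure or intolerance.

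**The concern.** The primary objective is whether suppression is sustained on DTG+RPV. The participants who bear most directly on that question are those whose suppression fails and who then come off the drug. Section 8.2 seems to keep them in the set, but being in the set is not a score. An analyst who then applies 10.2 and 10.3 finds no on-treatment value in the window and removes them from the denominator. The primary result would then omit failures that the study has on record.

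This is a single-arm study, so no comparator shares the same distortion, and the proportion is read at face value. A descriptive proportion still needs a defined numerator and denominator, and here the SAP leaves one foreseeable group without either.

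**Working it through.** **Step 1: the passages side by side.** Take a participant who stops DTG+RPV before day 1005 and is not lost to follow-up.

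| Reading | Basis | Result in the primary proportion |
|---|---|---|
| A | 8.2 keeps the participant; no qualifying value means no success | In the denominator, not suppressed |
| B | 10.2 requires an on-treatment value; 10.3 uses non-missing data only | Left out altogether |
| C | The on-treatment condition in 10.2 applies only to two or more assessments, so a single off-drug value counts | Scored on the HIV-RNA under another regimen |

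No passage says which reading prevails.

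**Step 2: reproduce the plan's figures.** Inputs from protocol 3.5 and SAP 7.2: 90% suppressed, 95% confidence, full interval width 0.10, at most 30% dropout.

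- The smallest n whose exact (Clopper-Pearson) interval at 0.90 has width at most 0.10 is 158 (width 0.0997). This matches the plan.
- 158 / 0.70 = 225.7, rounded up to 226. This also matches. The sample size is not in question.
- The planned half-width is 0.10 / 2 = 5 points.

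**Step 3: base case.** 226 × 0.70 = 158.2, so 158 evaluable. 158 × 0.90 = 142.2, so 142 suppressed. 142/158 = 89.9% (exact 95% CI 84.1 to 94.1). Under reading B the result stays here however many participants stop.

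**Step 4: add v virologic stoppers as not suppressed.** The formula is 142 / (158 + v). The documents give no v, so every value is an assumption.

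| v | Proportion | Exact 95% CI | Fall (points) |
|---|---|---|---|
| 1 | 142/159 = 89.3% | 83.4 to 93.6 | 0.6 |
| 3 | 142/161 = 88.2% | 82.2 to 92.7 | 1.7 |
| 5 | 142/163 = 87.1% | 81.0 to 91.8 | 2.8 |
| 9 | 142/167 = 85.0% | 78.7 to 90.1 | 4.8 |
| 10 | 142/168 = 84.5% | 78.2 to 89.6 | 5.3 |

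The fall first exceeds 5 points at v = 10, which is 10/226 = 4.4% of those enrolled.

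At the recruitment goal, 250 × 0.70 = 175 evaluable, and 158/175 = 90.3%. Then v = 1, 3 or 5 lowers the rate by 0.5, 1.5 or 2.5 points.

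**Step 5: the three readings on the same people.** Suppose 17 of the 226 − 158 = 68 participants without a year-3 value are known stoppers for any reason (one quarter, an assumption).

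- Reading A: 142/175 = 81.1% (CI 74.5 to 86.6).
- Reading B: 142/158 = 89.9%.
- Reading C, if all 17 are suppressed on a new regimen: (142 + 17)/175 = 159/175 = 90.9%.

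**The case against.** The strongest reply is that 8.2 is the specific rule, written with the primary endpoint in view, and that it favours reading A. It excludes a missing value only for those on the drug, and 11.3.1 lists only loss to follow-up. Someone in the set without a qualifying value is then naturally not a success. Reading B needs the general text of 10.3 to override 8.2, and needs the on-treatment wording of 10.2 to reach beyond the case of several assessments. This stands. A reader might infer that the SAP removes virologic failures from its primary result; the documents do not support that as a settled fact. They support only that the passages conflict and that one way of following them has this effect.

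A reader might also infer that the gap can only inflate the rate. It does not work in one direction only. Reading A lowers the rate, and it would also count people who stop for reasons unrelated to virology as not suppressed. Readings B and C can raise it.

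It is also tempting to cite the withdrawal for non-adherence in protocol 6.2.3 as a source of such participants. That rule concerns leaving the study. A withdrawn patient may still be on the drug, in which case the second exclusion in 8.2 may already apply. The point does not rest on it.

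Two further replies carry weight. The failures are not hidden: rebound and the composite endpoint in 11.3.2 run from baseline to year 3, and 11.3.5 lists virologic discontinuations. The study also tests no hypothesis. These limit the harm but do not define the primary proportion, and the composite mixes in intolerance.

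Finally, a data review meeting precedes database lock and could settle the matter. Its stated task is the modified full analysis set, however, not the scoring of the endpoint.

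**Conclusion.** The SAP needs a scoring rule for participants who stop DTG+RPV before the window and are not lost to follow-up. Section 8.2 implies that they stay in the set, 11.3.1 gives them no score, and 10.2 with 10.3 would drop them. If the last two govern, documented virologic failures are missing from the primary proportion and it is biased upward. If 8.2 is read as counting them as not suppressed, that bias is absent. If a lone off-drug value is accepted, success on another regimen could be credited to DTG+RPV. The passages must be reconciled.

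The size is unknown because every count above is assumed. At the plan's own 90% and 158 evaluable, up to 9 virologic stoppers move the rate by less than the planned half-width, and 10 or more exceed it. The 30% dropout behind these figures is a stated maximum. The point should be fixed, but it does not show that the reported rate will be wrong.

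**What to change.** State the following in SAP 8.2 and 11.3.1, and apply it to the year 1 and year 2 versions in 11.3.2:

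1. In the main analysis, participants who discontinued DTG+RPV for virologic reasons before the window, and whose last on-treatment HIV-RNA did not meet the endpoint definition, count as not suppressed. This overrides the non-missing denominator in 10.3. Requiring a failed last value ties the score to an observed result, so no HIV-RNA value is imputed.
2. HIV-RNA measured after stopping DTG+RPV is not used, even when it is the only value in the window.
3. Participants who stopped for other reasons and have no on-treatment year-3 value are shown by reason as 'no virologic data' and left out of the main proportion. One sensitivity result counts them as not suppressed. Virologic stoppers whose last value did meet the definition can be shown in the same category, so that nobody is left unassigned.

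Keep the 8.2 exclusion of participants lost to follow-up. A sensitivity result counting those whose last HIV-RNA failed the definition is optional.

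The cost is a few sentences and one or two table rows. The SAP 7.4 flow chart already collects HIV-RNA, the date and reason of study discontinuation, and the subsequent ART. It has no separate row for the DTG+RPV stop date, so the team should confirm how that date is recorded. The downside is that the headline rate may be slightly less favourable.
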